In this study, we aim to assess possible bioeffects that may be caused by the use of SWE with conditionally increased acoustic output pressure (CIO). Bioeffects will be monitored by a series of liver function tests (LFTs) with results graded according to the NCI scale for drug hepatotoxicity. LFTs will be collected prior to SWE imaging using CIO, as well up to 7 days post-imaging. Results will be compared to LFTs collected from the same patient after a washout period followed by standard SWE imaging. Secondarily, we aim to understand the degree to which SWE imaging results have improved with the use of COI.

[figure not shown]

Figure 1A. Standardized MI and TI display (red area) Ultrasound systems meeting the U.S. FDA 510(k) guidance for 'Track 3' systems will display TI and MI values on the ultrasound image. Figure 1B. Unreliable SWE measurement with high SCD value. Figure 1C, 1D: Poor region of interest (ROI) filling due to poor shear wave propagation. High skin to liver capsule distance may be an important factor for poor ROI filling.

b) Rationale behind the proposed research, and potential benefits to patients and/or society

As the use of the SWE, is a non-invasive, low-cost and widely available imaging diagnostic tool for liver fibrosis staging, and the acoustic and thermal limits in current FDA guidelines typically do not give reliable SWE measurements in obese patients with high skin-to-liver capsule distance

(SCD), our aim is to conditionally increase the acoustic pressure (CIO) of a SWE system to help clinicians obtain accurate SWE results in obese patients. We aim to reduce the need for monitoring hepatic fibrosis and steatosis using liver biopsy, as it is and costly, invasive with high morbidity and mortality rates, and is subject to sampling error.

2. Specific Aims and Objectives

Aim 1: Ascertain if hepatic bioeffects occur when increasing acoustic output above FDA limits for SWE imaging.

[figure not shown]
Aim 2: Determine if SWE image quality improves when using increased acoustic output.

Aim 3: Quantify the effect of phase aberration on SWE tracking.

Hypothesis: Increased acoustic output will improve SWE image quality without causing hepatic bioeffects.

3. General Description of Study Design

This is a prospective pre/post single arm non-inferiority study to show that the increase in liver function tests following increased acoustic output SWE is not more than two standard deviations.

4. Subject Selection

a) Inclusion criteria

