There are no expected direct benefits to the subjects participating in the study. Liver biopsy, the current gold standard test to assess fibrosis is imperfect, costly, invasive, and subject to sampling error. The imaging strategy that will be evaluated, increased output SWE, has the potential to reduce the number of liver biopsies performed for the diagnosis and monitoring of hepatic fibrosis and steatosis. Patients, particularly those who are obese, may potentially benefit in the future by having a better non-invasive test to stage their liver fibrosis and thus, may be spared more invasive testing.

9. Statistical Analysis

Three biomarkers based on liver function test which are associated with liver injury are used in our study[22].

Alanine transaminase (ALT). ALT is an enzyme found in the liver that helps convert proteins into energy for the liver cells. When the liver is damaged, ALT is released into the bloodstream and levels increase. The normal limit for ALT at MGH is 7 to 55 U/L[23, 24]. The standard deviation for ALT is 12 U/L[23, 24].

Aspartate transaminase (AST). AST is an enzyme that helps metabolize amino acids. Like ALT, AST is normally present in blood at low levels. An increase in AST levels may indicate liver damage, disease or muscle damage. The normal limit for AST at MGH is 10 to 40 U/L. The standard deviation for AST is 7.5 U/L.

Alkaline phosphatase (ALP). ALP is an enzyme found in the liver and bone and is important for breaking down proteins. Higher-than-normal levels of ALP may indicate liver damage or disease, such as a blocked bile duct, or certain bone diseases. The normal limit for ALP at MGH is 45 to 115 U/L. The standard deviation for ALP is 17.5 U/L.

The power calculations shown below are based on paired non-inferiority testing assuming no mean difference between pre and post imaging liver function tests and a non-inferiority margin of 1σ (1/2 upper limit of normal) with alpha = 0.05, target power = 0.9, and an assumed dropout rate of 25%[25]. For comparison, many drug trial use 5x the upper limit of normal as the criteria for drug hepatotoxicity. Our non-inferiority margin has been selected to be much more stringent given that ultrasound is an otherwise noninvasive diagnostic test.

Non inferiority margin	Assumed difference in mean	Standard deviation of biomarker	Sample size	Sample size + Dropout rate (25%)
$1\sigma = 12$	0	$1\sigma = 12$	18	24

10. Monitoring and Quality Assurance

a) Data integrity

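### Aim 1 asks whether hepatic bioeffects occur, but the only planned test compares the mean enzyme rise with a margin and never with zero, so a pass can support only 'mean rise below the margin'

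*Combined protocol and SAP*

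**What the plan says.** Section 2 states Aim 1 as a question about presence: "Ascertain if hepatic bioeffects occur when increasing acoustic output above FDA limits for SWE imaging". The hypothesis is "Increased acoustic output will improve SWE image quality without causing hepatic bioeffects".

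Section 9 contains the only inferential method: "paired non-inferiority testing assuming no mean difference between pre and post imaging liver function tests and a non-inferiority margin of" one standard deviation, which the same sentence equates with half the upper limit of normal, with alpha 0.05, power 0.9 and 25% dropout. The sample-size table works this through for ALT (margin 12, SD 12, assumed difference 0) and gives 18 subjects, or 24 with dropout. Section 3 sets a different limit: the rise in liver tests "following increased acoustic output SWE is not more than two standard deviations".

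Two other read-outs are mentioned. Section 10c grades liver tests on the NCI scale, starting at the upper limit of normal. Section 1a mentions a comparison with tests taken after a washout and standard SWE; it names no test, and the visit schedule in Section 6 has no such visit. Neither is a comparison of the mean change with zero.

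**The concern.** The question and the test do not match. A non-inferiority test asks whether the mean rise is smaller than a chosen amount. It does not ask whether there is a rise. As written, the trial could pass on data that themselves show enzymes going up after imaging above the FDA limit. It could also fail with no evidence of any rise, and the plan has no wording that separates that result from a demonstrated rise.

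NCI grading does not fill the gap. Its first grade begins at the upper limit of normal (55 U/L for ALT), and Section 4b excludes people with recent values above that limit. A modest shift shared by all subjects would mostly stay ungraded.

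**Working it through.** **Inputs from the documents.** ALT margin 12 U/L, SD 12 U/L, assumed difference 0, alpha 0.05, power 0.9, n=18 (all Section 9). Whether alpha is one- or two-sided is not stated.

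**Reproducing the plan's figure.** Treat 12 as the SD of a single measurement with no correlation between a subject's pre and post values:
- SD of change = 12 × √2 = 17.0 U/L.
- n = 2 × (1.645 + 1.282)² × (12/12)² = 17.1, rounded up to 18; 18/0.75 = 24.

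So 18 and 24 reproduce with a one-sided 0.05. With the t distribution, power at n=18 is 0.891. A one-sided 0.025 gives 22 (normal) or 24 (t), and an SD of change of 12 gives 9 or 11. Neither of these alternatives matches the table.

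**SD of change.** It is not given, so a range is used. With pre/post correlation ρ, SD of change = 12 × √(2(1 − ρ)):
- ρ = 0: 17.0
- ρ = 0.50: 12
- ρ = 0.78: 8
- ρ = 0.875: 6

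**Rules** (n=18, 17 df, SE = SD/√18):
- Pass: mean + 1.740 × SE < 12.
- Rise shown: mean − 2.110 × SE > 0 (two-sided 95% lower limit).

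With the SE at its expected value:

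| SD of change | SE | Largest mean that passes | Smallest mean that shows a rise |
|---|---|---|---|
| 17 | 4.00 | 5.04 | 8.44 |
| 12 | 2.83 | 7.08 | 5.97 |
| 8 | 1.89 | 8.72 | 3.98 |
| 6 | 1.41 | 9.54 | 2.98 |

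Both can hold together when 12 > (1.740 + 2.110) × SD/√18, that is, when the SD of change is below 12 × 4.243/3.850 = 13.2 U/L.

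**Simulation** (normal changes, 400,000 trials per setting):

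| SD of change | Pass, true rise 6 | Pass and rise shown, true rise 6 | Pass, true rise 9 | Pass, true rise 11 |
|---|---|---|---|---|
| 17 | 42% | 1% | 18% | 8% |
| 12 | 65% | 21% | 27% | 10% |
| 8 | 92% | 77% | 45% | 13% |
| 6 | 99% | 97% | 65% | 17% |

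With a one-sided 95% lower limit, the third column becomes 3%, 31%, 84% and 98%.

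**Failures.** At SD 17 and no true effect, 10.9% of trials fail. A rise is shown in 2.5% of all trials, and 0.3% both pass and show a rise, so 2.2% fail with a rise shown. The other 10.9 − 2.2 = 8.7% fail with no rise shown and are simply inconclusive.

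**Two-SD limit.** Under Section 3 the ALT margin would be 24 U/L. A true rise of 12 U/L would then pass 89% of the time at SD 17 and 99% at SD 12.

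**The case against.** **A small rise inside the margin is what non-inferiority accepts.** Section 3 frames the study as bounding the increase, and a pass does exclude a mean rise above the margin. This stands. The test is a sound answer to a bounded question; the mismatch is with the aim and the hypothesis.

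**A reader might infer that any mean rise under 12 U/L passes.** It does not. The upper confidence limit, not the mean, must be under 12. At SD 17 the observed mean must be about 5 U/L or less, and a true rise of 9 passes only 18% of the time.

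**A reader might infer that the plan will report a pass as 'no bioeffects'.** No section states how a pass will be worded. That link comes only from the hypothesis, and Section 10c ties bioeffects to graded values above normal.

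**The large percentages need SDs that the documents do not give.** This is correct. At the SD implied by n=18, a pass that also shows a rise almost never happens. Stable medication and resampling within about nine days make some positive correlation a reasonable assumption, but it is not documented.

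**A paired test already yields the mean and its standard error.** It does, so the lower limit can be had without new data. But the plan does not commit to reporting it or say how it will be read.

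**A rise would not prove a device effect.** This stands. The study has one arm, and conventional SWE is done at the same visit, so drift, regression to the mean or the standard scan could also explain it.

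**Conclusion.** The concern holds in a limited form. The documents plan no test or interval against zero, so a pass can support 'mean rise below the margin' but not the hypothesis as worded. A real shared rise can pass: for 6 U/L of ALT, 42% of the time at the SD of change implied by n=18, and 65% to 99% if that SD is between 12 and 6 U/L. A pass on data that also show a rise is rare at SD 17 (1%) and common only if the SD is well below 13 U/L. These figures assume n=18, a margin of 12 U/L, a one-sided 0.05 test, normal changes and the same true rise in every subject.

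The margin itself is not settled. Section 3 says two SD and Section 9 says one. Section 9 also equates one SD with half the upper limit of normal, which for ALT is 55/2 = 27.5 U/L, not 12. These must be reconciled; a wider margin enlarges the gap described here. This is a cheap improvement to what the trial can conclude, not a flaw that invalidates the design.

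**What to change.** In Section 9, report the mean paired change in ALT, AST and ALP at days 1, 2 and 7 with two-sided 95% confidence intervals, and read each against both zero and the margin:

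- Upper limit below the margin: 'mean rise below the margin', not 'no hepatic bioeffects'.
- Lower limit above zero: 'mean rise after imaging detected', without attributing it to the increased output. This is added to the statement about the margin, whether the margin is excluded or not.
- Interval that includes both zero and the margin: 'inconclusive'.

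State the level at which the upper limit is compared with the margin. One-sided 0.05 reproduces n=18; the upper end of a two-sided 95% interval is stricter. Settle on one margin across Sections 3 and 9.

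The cost is a few sentences, with no extra subjects, visits or blood. The downside is chance findings. Each of the nine comparisons has a 2.5% chance of a lower limit above zero with no true change, or 1 − 0.975⁹ = 20% for at least one if they were independent. Simulation under assumed correlations (0.5 between days, 0 to 0.6 between markers) gives 15% to 18%. Name one primary marker and day, or label the others descriptive, and state this rate in the report.

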Any possible bioeffects that may be caused by SWE imaging with CIO will be monitored and determined by liver function test (LFT), with results graded according to the NCI scale for drug hepatotoxicity (grade 1 = 1-3x upper limit of normal; grade 2 = 3-5x upper limit of normal; grade 3 = 5-20x upper limit of normal; grade 4 = >20x upper limit of normal). Participants will attend study visits to obtain blood samples collected 1 day post-scanning, 2 days post-scanning, and 7 days post-scanning to trend liver function tests and assess laboratory value normalization.

d) Adverse event reporting guidelines

The PI will be responsible for safety monitoring of enrolled subjects during the study period. Subjects will be evaluated for signs of pain and discomfort before, during, and immediately after the study visit. Any significant adverse event will be reported to the IRB and followed up by the study staff.

All Adverse Events, Serious adverse events, Adverse Device Effects, and Device Deficiencies will be collected at the time of reporting by the subject or when detected by the Investigator. They will be source documented and maintained as part of the study record.

An assessment of the following metrics will be made by the Investigator for each Adverse Event:

- severity,
- seriousness,

- anticipated or unanticipated,
- relation to study participation or investigational imaging technique,
- action taken,
- outcome (resolution, sequelae, etc.)

Definition of adverse events (AE) in this study will be "any untoward or unfavorable medical occurrence in a human subject, including any abnormal physical exam or certain unexpected abnormal laboratory finding, symptom, or disease, temporally associated with a subject's participation in the research".

Definition of serious adverse events (SAE) in this study:

A SAE is any AE that:

Results in death, or

Is life-threatening, or

Results in hospitalization or prolongation of existing hospitalization, or

Results in a persistent or significant disability/incapacitation, or

May jeopardize the participant's health and may require medical or surgical intervention to prevent one of the other outcomes listed above. No SAEs are anticipated in this study.

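### Section 3 sets the non-inferiority margin at two SDs, Section 9 sizes the trial on one SD, and one SD is not half the upper limit of normal

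*Combined protocol and SAP*

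**What the plan says.** Section 3 (General Description of Study Design) describes a single-arm pre/post non-inferiority study intended to show that the "increase in liver function tests following increased acoustic output SWE is not more than two standard deviations".

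Section 9 (Statistical Analysis) describes the power calculation as a paired non-inferiority test with zero true mean difference, 25% dropout and "a non-inferiority margin of 1σ (1/2 upper limit of normal) with alpha = 0.05, target power = 0.9". The table beneath gives margin 1σ = 12, SD 1σ = 12, sample size 18, and 24 after dropout. Only ALT values are tabulated.

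The same section supplies the reference limits and SDs:

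- ALT: "The normal limit for ALT at MGH is 7 to 55 U/L" and "The standard deviation for ALT is 12 U/L".
- AST: "The normal limit for AST at MGH is 10 to 40 U/L. The standard deviation for AST is 7.5 U/L".
- ALP: "The normal limit for ALP at MGH is 45 to 115 U/L. The standard deviation for ALP is 17.5 U/L".

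It then defends the choice: "Our non-inferiority margin has been selected to be much more stringent", by comparison with a criterion of five times the ULN in drug trials. Section 10(c) adds that bioeffects will be monitored through liver function tests, "with results graded according to the NCI scale for drug hepatotoxicity".

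**The concern.** Aim 1 asks whether output above the FDA limits causes hepatic bioeffects, and the non-inferiority margin decides that question. The document gives two margins a factor of two apart and does not say which one the final analysis tests. An observed mean rise lying between the two pass limits would fail under Section 9 and pass under Section 3, so the threshold could be chosen after the data are seen. The Section 3 version would also usually accept a true mean rise equal to the one the trial was sized to exclude.

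The parenthesis in Section 9 does not settle the matter. It fits neither margin and points to a number larger than both. The NCI grading does not settle it either, because it classifies individual values against multiples of the ULN and sets no limit on a mean rise.

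**Working it through.** **Inputs.** From Section 9: SDs of 12, 7.5 and 17.5 U/L; reference ranges 7–55, 10–40 and 45–115 U/L; alpha 0.05; power 0.9; true difference 0; dropout 25%. From Section 3: a margin of two SDs. Two inputs are not stated. Alpha is taken as one-sided, which reproduces the stated sample size. The SD of the pre/post change is taken over an illustrative range: 1σ (correlation 0.5) to √2σ (correlation 0), that is 12 to 16.97 U/L for ALT.

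**1. The stated sample size.** Normal approximation: n = ((1.645 + 1.282) × SD of change / margin)².

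- One-SD margin, SD of change √2 × 12 = 16.97: (2.927 × 16.97 / 12)² = 17.13, rounded up to 18. Dropout: 18 / 0.75 = 24. Both stated figures reproduce. (The exact t calculation gives 19; power at 18 is 0.891.)
- Two-SD margin, same SD of change: (2.927 × 16.97 / 24)² = 4.28, so 5 (exact t: 6).
- Two-SD margin at the largest possible SD of change (2σ = 24, correlation −1, equal variances before and after): 8.56, so 9 (exact t: 11).

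Of the two margins, only one SD yields 18.

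**2. The parenthesis.**

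| | 1 SD | ULN | 1 SD / ULN | 2 SD / ULN | ULN/2 | ULN/2 in SDs | Range / 4 |
|---|---|---|---|---|---|---|---|
| ALT | 12 | 55 | 0.218 | 0.436 | 27.5 | 2.29 | (55−7)/4 = 12 |
| AST | 7.5 | 40 | 0.188 | 0.375 | 20 | 2.67 | (40−10)/4 = 7.5 |
| ALP | 17.5 | 115 | 0.152 | 0.304 | 57.5 | 3.29 | (115−45)/4 = 17.5 |

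Neither one nor two SDs is half the ULN for any biomarker. Each SD is exactly a quarter of the reference range, so one SD is half the distance from the range midpoint to the ULN. The parenthesis may be a garbled form of that, but the text does not say so. It is a mistaken description of 1σ, not a third margin.

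**3. Largest observed mean rise that passes at n = 18.** Limit = margin − t(0.95, 17) × SD of change / √18, with t = 1.740. For ALT the subtracted term is 1.740 × 12 / 4.243 = 4.92, or 1.740 × 16.97 / 4.243 = 6.96.

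| | Margin 1 SD (SD of change 1σ; √2σ) | Margin 2 SD (SD of change 1σ; √2σ) |
|---|---|---|
| ALT, U/L | 7.08; 5.04 | 19.08; 17.04 |
| AST, U/L | 4.42; 3.15 | 11.92; 10.65 |
| ALP, U/L | 10.32; 7.35 | 27.82; 24.85 |

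At any given SD of change the two limits differ by exactly one SD of the biomarker (12 U/L for ALT).

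**4. Chance of declaring non-inferiority when the true mean ALT rise is 12 U/L.** Noncentral t with 17 df and noncentrality (margin − 12) × √18 / SD of change.

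- One-SD margin: noncentrality 0, probability 0.050.
- Two-SD margin, SD of change 12: noncentrality 12 × 4.243 / 12 = 4.24, probability 0.992.
- Two-SD margin, SD of change 16.97: noncentrality 12 × 4.243 / 16.97 = 3.00, probability 0.891.

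**The case against.** The strongest reply is that Section 9 is the dedicated statistical section and gives 1σ in both text and table, while Section 3 is a one-sentence overview that neither uses the word margin nor says which SD it means. The sample size is adequate either way. Nothing is calculated from half the ULN, so the parenthesis is only a wording slip. The claim of stringency is made against five times the ULN (275 U/L for ALT), and a 24 U/L margin meets it as well.

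Much of this stands. The sample size is not in error, the parenthesis alone would be minor, and the stringency sentence does not contradict either margin. The 24 U/L figure is an inference from the Section 9 SD. It is also fair that repeat measurements in the same people within days may correlate above 0.5. At an assumed correlation of 0.8 the ALT pass limits become 8.9 and 20.9 U/L, and at 0.9 they become 9.8 and 21.8, so the ranges above are illustrations, not bounds. The 12 U/L gap between the limits is unchanged.

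What does not stand is treating Section 3 as loose description. It is a numerical threshold in the sentence that says what the non-inferiority study is to show, and no text subordinates it to Section 9. That 18 matches one SD shows which margin the table used; it does not tell a reader which threshold will support the conclusion.

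**Conclusion.** The concern holds, and the text is wrong as written. The document states two non-inferiority thresholds for the same claim, 12 and 24 U/L for ALT, and equates 1σ with half the ULN when its own figures make it about 22%, 19% and 15% of the ULN for ALT, AST and ALP.

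The consequence is an ambiguous success criterion, not a loss of power. The factor of two and the error in the parenthesis follow from the document's figures alone. The pass limits and probabilities rest on 18 evaluable subjects, one-sided 5% and the assumed SD of change. They apply to one biomarker at one time point; the plan does not say how three biomarkers and three post-imaging draws are combined.

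**What to change.** State one margin, identically in Sections 3 and 9, in U/L for each biomarker. The margin that matches the sample-size table is one SD: 12 U/L for ALT as tabulated and, from the stated SDs, 7.5 for AST and 17.5 for ALP. On that choice, Section 3 changes from two standard deviations to one. If the investigators intend two, Section 9 must say so and justify it, and its table no longer describes the test.

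Delete the parenthesis about half the ULN, or replace it with the correct shares (about 22%, 19% and 15%). State the SD of change behind the 18 (√2 × 12 = 16.97 U/L reproduces it) and that alpha is one-sided.

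With the one-SD margin, this is a wording amendment to two sections. Sample size and procedures do not change, and the only cost is a stricter claim in Section 3. It should be made before anyone looks at the outcome data.
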